### **5.7.3 Caregiver Impression of Investigational Medicinal Product Palatability**

The caregiver's impression of palatability of the IMP will be assessed at Visit 8 (end of treatment). The Caregiver will be asked the following question to be rated on a 5-point scale:

- Overall, how acceptable did your child find the study medication?

The possible responses are: Liked it a lot; Liked it; Neither liked nor disliked it; Didn't like it; Didn't like it at all.

The caregiver's impression of palatability of the IMP will be summarized, on a categorical scale, by treatment group.

### **5.7.4 Study Medication Use and Behavior Survey**

This form consists of 18 questions regarding the use of the IMP. The trained investigator or study coordinator will complete this survey as an interview with the patient/caregiver at the final dosing visit (Visit 8 or Visit 9, as applicable).

The form will be completed for all patients 12 years of age and older in the study.

Each question will be summarized, on a categorical scale, by treatment group. Percentages will be based on the number of patients completing the survey, in each treatment group. The summary will be presented separately for all patients with a completed form and patients 12 years of age and older.

### **5.7.5 Supplemental Drug Accountability Form**

This form consists of 7 questions regarding various aspects of drug accountability and patient usage. It is completed as part of an interview with the patient/caregiver when a triggering drug accountability discrepancy is identified.

The triggering drug accountability discrepancies are as follows:

- Missing bottle(s).
- Compliance issues where one or more bottles are used compared to what was the expected use, according to the IVRS report and paper diary.
- Returned IMP supply with evidence of tampering.
- Greater than the target daily dose as recorded in the IVRS report and paper diary.

The number of patients completing a form will be summarized by treatment group. The summary will be presented separately for all patients with a completed form and patients 12 years of age and older.

### **5.7.6 Supplemental Adverse Event Form**

This form consists of 15 questions regarding the AE and use of IMP. It is completed as part of an interview with the patient/caregiver when a triggering AE of interest is reported.

The categories for triggering AEs of interest are:

- Euphoria or inappropriate elation.
- Inappropriate laughter or exhilaration.
- Mood changes.
- Drunk, high or intoxicated.
- Hallucinations (visual or auditory), dissociations, disorientation, agitation.
- Disturbance in cognition, memory, or attention.
- Drug abuse.
- Drug withdrawal or drug withdrawal syndrome.
- Addiction.
- Overdose.
- Misuse of IMP.
- Thoughts of suicide, attempted suicide or suicide.

The number of patients completing a form will be summarized by treatment group. The summary will be presented separately for all patients with a completed form and patients 12 years of age and older.

### **5.7.7 Site Classification Form**

The investigator reviews the applicable Supplemental Adverse Event Form or Supplemental Drug Accountability Form, and then completes a Site Classification Form. For each Supplemental Adverse Event Form or Supplemental Drug Accountability Form completed, there should be an associated Site Classification Form.

The Site Classification Form requires the investigator to assign the finding to an appropriate classification and then to also assign the possible relationship to the IMP. The investigator is also required to indicate the level of the certainty of the classification.

The number of patients completing a form and the possible relationship and level of the certainty for each category will be summarized, on a categorical scale, by treatment group. If more than one form is completed for a particular patient then they will be summarized under each category for all forms. However, if more than one form is completed with and assigned to the same category, then 'related' would be used over 'not related' and the highest level of certainty will be used for the corresponding chosen relationship. The summary will be presented separately for all patients with a completed form and patients 12 years of age and older.

### **5.7.8 IVRS Compliance**

The number of unreported days in IVRS, during the baseline and treatment periods, will be summarized, on a continuous and categorical scale, by treatment group for patients in the ITT analysis set. For the summary on a continuous scale, the lower and upper quartiles will also be presented.

The percentage IVRS compliance, during the baseline and treatment periods, will also be summarized, on a continuous and categorical scale, and calculated as:

$$\left[ \frac{\text{Number of reported days in IVRS}}{\text{Number of reported days in IVRS} + \text{Number of unreported days in IVRS}} \right] \times 100$$

### **5.7.9 Meal Times**

Patient meal times will be recorded for the day prior to and the day of Visit 2 (Day 1) and Visit 8 (end of treatment). Meal times will be listed only.

## 5.8 Changes in the Conduct of the Study or Planned Analysis

The identification of 3 key secondary endpoints and the hierarchical testing procedure were not defined in the protocol, but have been included in the SAP prior to unblinding.

Upon blinded review of IVRS data for the number of convulsive seizures greater than 30 minutes in duration and the number of non-convulsive seizures greater than 30 minutes in duration, it was determined that there were insufficient numbers of patients reporting these seizures to perform analyses planned in the protocol.

Upon blinded review of the number of patients with inpatient epilepsy-related hospitalizations, it was determined that there were insufficient numbers of patients to perform analyses planned in the protocol.

The protocol included changes from baseline in usage of rescue medication as an efficacy endpoint. However, due to inconsistencies in the collection of this data, no analyses are proposed.

The endpoint of number of patients experiencing a >25% worsening, -25 to +25% no change, 25–50% improvement, 50–75% improvement or >75% improvement in convulsive seizures from baseline has been updated to the following:

- Number of patients experiencing a >25% increase,  $\geq 0$  to  $\leq 25\%$  increase, >0 to <25% reduction,  $\geq 25$  to <50% reduction,  $\geq 50$  to <75% reduction or  $\geq 75\%$  reduction in convulsive seizures from baseline.

## 7. AMENDMENTS

Notable changes to the SAP that were completed prior to unblinding, are given below.  
Minor changes, clarifications and corrections are not listed.

Date	Section	Description of Change
-------------	----------------	------------------------------

## 8. ATTACHMENTS AND APPENDICES

### Appendix 1 Adverse Events of Special Interest – Abuse Liability

---

Withdrawal	Drug withdrawal convulsions
	Drug withdrawal headache
	Drug withdrawal maintenance therapy
	Drug withdrawal syndrome
	Drug withdrawal syndrome neonatal
	Drug rehabilitation
	Rebound effect
	Steroid withdrawal syndrome
	Withdrawal arrhythmia
	Withdrawal syndrome
Drug abuse and dependence	Dopamine dysregulation syndrome
	Drug abuse
	Drug abuser
	Drug dependence
	Drug dependence, antepartum
	Drug dependence, postpartum
	Intentional drug misuse
	Intentional overdose
	Maternal use of illicit drugs
	Neonatal complications of substance abuse
	Polysubstance dependence
	Substance abuse
	Substance abuser
	Accidental overdose
	Dependence
	Disturbance in social behaviour
	Drug administered at inappropriate site
	Drug detoxification
	Drug diversion
	Drug level above therapeutic
	Drug level increased
	Drug screen
	Drug screen positive
	Drug tolerance
	Drug tolerance decreased
	Drug tolerance increased
	Medication overuse headache
	Narcotic bowel syndrome
	Needle track marks
	Overdose
	Prescribed overdose
	Prescription form tampering
	Substance use
Substance-induced mood disorder	
Substance-induced psychotic disorder	
Toxicity to various agents	

---

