## **8.2 Concomitant Therapy**

It is theoretically possible that GWP42003-P may modify the metabolism of other drugs (including AEDs) administered concurrently and there remains the possibility of pharmacological interactions between GWP42003-P and other concurrently administered drugs. Doses of any concomitant AEDs must have been stable for at least four weeks prior to screening and must remain stable throughout the study period. If there are any clinical symptoms of concern, thought to be linked to interaction of IMP with other AEDs then this should be discussed with the GW medical monitor. Adjustments to AEDs are permitted in these cases of safety concern. Any changes to AEDs must be recorded in the CRF. Further information on drug interactions can be found in the Investigator Brochure (IB).

The use of rescue medication is allowed when necessary. Any medication, other than the IMP, taken during the study must be recorded on the Case Report Form (CRF).

Any non-pharmacological therapies (e.g., ketogenic diet, VNS) must also be stable up to four weeks prior to screening and throughout the duration of the study.

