##### **9.1.16.1.1 List of 'Triggering Adverse Events of Interest'**

During the collection of AEs, if the patient reports an AE consistent with any of the following categories, then the investigator or study coordinator is required to complete an

additional Supplemental Adverse Event Form and a Site Classification Form (investigator only) following further discussion of the event(s) with the patient or their caregiver. The categories are:

- Euphoria or inappropriate elation.
- Inappropriate laughter or exhilaration.
- Mood changes.
- Drunk, high or intoxicated.
- Hallucinations (visual or auditory), dissociations, disorientation, agitation.
- Disturbance in cognition, memory, or attention.
- Drug abuse.
- Drug withdrawal or drug withdrawal syndrome.
- Addiction.
- Overdose.
- Misuse of IMP.
- Thoughts of suicide, attempted suicide or suicide.

An AE that is consistent with the above categories will be known as a ‘triggering AE of interest’ for the purposes of this study.

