For the summary of TEAEs by time to AE resolution, data will be summarized under the following categories:

- 1 week ( $\leq 7$  days).
- 2 weeks (8–14 days).
- 3 weeks (15–21 days).
- 4 weeks (22–28 days).
- >4 weeks (>28 days).
- Ongoing (for AEs not resolved).

The time to AE resolution will be calculated for TEAEs as:

$$\text{Stop date of AE} - \text{Start date of AE} + 1$$

If patients have multiple occurrences of an AE then the AE will be counted once for the occurrence with the longest time to AE resolution. However, if any of the AEs are not resolved then the AE will be counted once within the 'Ongoing' category.

The start and stop day of the AE relative to the first dose of IMP (as recorded on the CRF) will be calculated as per Section 5.1.2. For partial dates, if it is clear from the partial date that the start/stop day was prior to the first dose of IMP, then 'pre' will be listed, similarly if it is clear that the event was post the first dose of IMP then 'post' will be listed as the start/stop day as appropriate.

All AEs will be listed. Listings will include the start and stop day of the AE, a flag for treatment emergence, and limited demographic information about the patient (age, sex, race and weight at screening). A separate listing will be provided for pre-treatment AEs, serious AEs and events of special interest (see [Appendix 1](#)).

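### The SAP's abuse-liability term list does not match the protocol's 12 triggering categories: seven have no term that directly names them, three have none on any reading, and no output groups AEs by category and arm

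*SAP*

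**What the plan says.** Abuse liability is a named safety variable in both documents (Protocol 4.1.2, SAP 3.3.3).

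Protocol 9.1.16.1.1 requires a Supplemental Adverse Event Form and a Site Classification Form "if the patient reports an AE consistent with any of the following categories". Twelve categories follow, among them "Euphoria or inappropriate elation", "Inappropriate laughter or exhilaration" and "Hallucinations (visual or auditory), dissociations, disorientation, agitation". The parent section, 9.1.16, is headed as applying from 12 years of age. SAP 5.7.6 repeats all 12 categories.

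The SAP selects its special-interest events from another list. Section 5.6.2 says: "A separate listing will be provided for pre-treatment AEs, serious AEs and events of special interest", and points to Appendix 1. That appendix has two groups, withdrawal and drug abuse/dependence, and produces Listing 11.1.2. Its terms include "Drug level increased". Protocol 8.2 states: "It is theoretically possible that GWP42003-P may modify the metabolism of other drugs (including AEDs) administered concurrently".

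For the supplemental AE forms, SAP 5.7.6 plans this output: "The number of patients completing a form will be summarized by treatment group". SAP 5.7.7 summarizes the investigator's classification, relationship and certainty by treatment group. SAP 5.6.2 tabulates all TEAEs by arm, system organ class and preferred term.

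**The concern.** The one AE output labelled abuse liability is driven by terms for withdrawal, dependence, overdose and misuse. The protocol's list also covers acute psychoactive effects: elation, intoxication, hallucination and disturbed cognition. Someone who opens Listing 11.1.2 expecting the protocol's signals would not find most of these. To compare arms on them, that reader would have to collect preferred terms by hand from the general TEAE tables, choosing the grouping after seeing the data.

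The problem is greater in younger patients. The trigger process is not required under age 12, which leaves out the whole 2–5 stratum and ages 6 to 11 of the 6–12 stratum. In the other direction, the drug-level and toxicity terms are not tied to the study drug, so an event about a concomitant antiepileptic drug (AED) could be listed under abuse liability.

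**Working it through.** There is no plan figure to reproduce. The check compares the two lists.

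**Step 1: size of each list.** Protocol 9.1.16.1.1 has 12 categories. Appendix 1 has 10 terms under withdrawal and 36 under drug abuse and dependence: 10 + 36 = 46.

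**Step 2: mapping.** A direct match is a term that names the category's event, with dependence accepted for addiction. A loose match is a related diagnosis.

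| Protocol category (shortened) | Direct match in Appendix 1 | Loose match |
|---|---|---|
| Euphoria, elation | none | none |
| Laughter, exhilaration | none | none |
| Mood changes | none | *Substance-induced mood disorder* |
| Drunk, high | none | *Toxicity to various agents* |
| Hallucination, dissociation, disorientation, agitation | none | *Substance-induced psychotic disorder* |
| Cognition, memory, attention | none | none |
| Drug abuse | yes | – |
| Withdrawal | yes | – |
| Addiction | yes (dependence terms) | – |
| Overdose | yes | – |
| Misuse | yes | – |
| Suicidality | none | *Intentional overdose* |

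*Disturbance in social behaviour* names none of the 12 categories and is not counted as a match.

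**Step 3: counts.**
- Direct mapping: 5 matched, 12 − 5 = 7 unmatched.
- Accepting the mood and psychotic disorder terms: 7 − 2 = 5 unmatched.
- Also accepting toxicity for intoxication: 5 − 1 = 4.
- Also accepting intentional overdose for suicidality: 4 − 1 = 3.

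The gap is therefore 3 to 7 of 12. The loose matches are weak. A substance-induced psychotic disorder already attributes the event to a substance, so it would not pick up an AE coded as agitation or disorientation. Intentional overdose does not pick up suicidal thoughts.

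**Step 4: where the unmatched events go.**
- General TEAE tables (SAP 5.6.2): all ages, by arm, but by preferred term and system organ class.
- Supplemental AE Form (SAP 5.7.6): number of patients with a form, not patients per triggering category.
- Site Classification Form (SAP 5.7.7): by arm and classification, only once a form has been triggered.
- Study Medication Use and Behavior Survey (SAP 5.7.4): by arm and question, planned from age 12.
- C-SSRS (SAP 5.6.4.4): suicidal ideation and behavior by arm, from age 6 in patients able to answer.
- Adjudication Committee (Protocol 9.1.16.5): reviews triggered cases and writes a report, but as written assesses only patients who completed the study.

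No entry in the SAP's table list groups AEs by the 12 categories and arm.

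**Step 5: terms not limited to the study drug.** Two of the 46 terms name a drug level: *Drug level increased* and *Drug level above therapeutic*. *Toxicity to various agents* is a third by inference. Protocol 9.1.10 measures AED levels at Visits 2, 4, 6 and 8, and Protocol 12.1.1 counts abnormal laboratory findings as possible AEs. Under Protocol 9.1.9 a laboratory result is recorded as an AE only if it is considered to represent one. The route into the listing exists, but the documents give no frequency for it.

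**The case against.** The strongest reply is that the two lists serve different purposes. The 12 categories trigger an interview, after which the site and then a committee classify the case. They do not define a confirmed abuse event. Appendix 1 is a term list for one listing, and neither document says that it must implement the protocol's categories. This stands as a reason not to call the mismatch an error of analysis. It does not explain why the only AE output for a named safety variable leaves out events that the protocol itself treats as possible signals.

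The reply also holds that the omitted events are reported elsewhere. That is correct, as Step 4 shows. SAP 5.7.6 and 5.7.7 also summarize any completed form, whatever the patient's age, beside the group aged 12 and older. What these outputs do not give is a by-arm count per category, or any required form under age 12.

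Two stronger readings are tempting. A reader might infer that abuse signals would be missed by the trial. The documents do not support this, because the events still appear by arm in the TEAE tables and in the full TEAE listing. A reader might also infer that AED interactions would produce a false excess in the active arms. The documents do not support that either. Appendix 1 yields a listing with no rate or test, Protocol 8.2 calls an interaction only theoretically possible, AED concentrations have their own summary (SAP 5.7.2), and a raised level must first be judged an AE.

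**Conclusion.** The mismatch is real and limited. Seven of 12 protocol categories have no term in Appendix 1 that directly names them. Three have none on any reading: euphoria/elation, laughter/exhilaration and cognition/memory/attention. The count of seven assumes direct naming; with the loosest related diagnoses it falls to three.

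The practical gap is that no planned output groups AEs by abuse-signal category and arm, and the trigger process is not required under age 12. Entry of AED-related events into the listing is possible, with unknown frequency. No efficacy result, alpha allocation or formal safety comparison is affected. The change is worth making because it improves the assessment of a named safety variable at little cost.

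**What to change.** Before unblinding:

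1. Extend Appendix 1 so that each of the 12 categories in Protocol 9.1.16.1.1 maps to stated MedDRA v17.1 preferred terms.
2. Add one table of patients with any TEAE in each category, by treatment arm, for all ages and for patients aged 12 and older.
3. In Listing 11.1.2, flag whether *Drug level increased*, *Drug level above therapeutic* and *Toxicity to various agents* concern the study drug or another drug.

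The cost is a term mapping, one table and one flag, from AE data already collected. The flag may need a check of the reported event text. The downside is that a wider list also catches mood and behavior events common in this population, so the counts mean little alone and must be read against placebo. The by-arm table allows that.

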## Appendix 2 Ranges for Clinically Significant Changes and Other Defined Flagged Values in Vital Signs

The range of values that will be used to identify clinically significant changes in vital signs parameters (See Section 5.6.4.1) are presented in Table 8.

**Table 8 Ranges for Potentially Clinically Significant Changes in Vital Signs**

Vital Sign	Range
Sitting Systolic BP	Change: < -20, > 20
Sitting Diastolic BP	Change: < -10, > 10
Pulse Rate	Change: < -10, > 10
Weight	Percent Change: $\leq -7, \geq 7$

Defined flagged values that will be used to identify low or high vital signs parameters (See Section 5.6.4.1) are presented in Table 9.

**Table 9 Other Defined Flagged Values for Vital Signs**

Vital Sign	Flag
Sitting Systolic BP	< 90, > 140, > 160
Sitting Diastolic BP	< 50, > 90, > 100
Pulse Rate	< 60, > 100
Temperature	> 38.0, < 36.0
Respiratory Rate	< 12, > 20

## Appendix 3 Defined Flagged Values in ECG Parameters

Defined flagged values that will be used to identify low or high ECG parameters (See Section 5.6.4.2) are presented in Table 10.

**Table 10 Defined Flagged Values for ECG Parameters**

ECG Parameter	Flag
QTc	> 450, > 480, > 500

#### Appendix 4 Toxicity Criteria for Laboratory Parameters

The toxicity criteria that will be used to identify abnormal laboratory parameters are presented in [Table 11](#) and [Table 12](#).

**Table 11 Toxicity Criteria for Biochemistry Parameters**

Parameter	Toxicity Decrease	Toxicity Increase
Chloride	$\leq 0.96 \times \text{LL}$	$\geq 1.04 \times \text{UL}$
Calcium	$\leq 0.89 \times \text{LL}$	$\geq 1.16 \times \text{UL}$
Sodium	$\leq 0.96 \times \text{LL}$	$\geq 1.04 \times \text{UL}$
Potassium	$\leq 0.90 \times \text{LL}$	$\geq 1.10 \times \text{UL}$
Glucose (mmol/L)	$\leq 3.2$	$\geq 16$
Phosphate	$\leq 0.79 \times \text{LL}$	
Cholesterol	$\leq 0.85 \times \text{LL}$	$\geq 1.6 \times \text{UL}$
AST		$\geq 3 \times \text{UL}$
ALT		$\geq 3 \times \text{UL}$
Lactate Dehydrogenase		$\geq 2.6 \times \text{UL}$
Alkaline phosphatase		$\geq 2 \times \text{UL}$
Gamma GT		$\geq 2.6 \times \text{UL}$
Bilirubin		$> 2 \times \text{UL}$
Albumin	$\leq 0.84 \times \text{LL}$	
Total protein	$\leq 0.84 \times \text{LL}$	$\geq 1.16 \times \text{UL}$
Urea		$\geq 2.6 \times \text{UL}$
Blood urea nitrogen		$\geq 2.6 \times \text{UL}$
Creatinine		$\geq 2.6 \times \text{UL}$
Uric acid		$\geq 1.16 \times \text{UL}$

UL = upper limit of reference range

LL = lower limit of reference range

**Table 12 Toxicity Criteria for Hematology Parameters**

Parameter	Toxicity Decrease	Toxicity Increase
Hemoglobin (g/dL)	$\leq 9.4$	
Hematocrit (%)	$\leq 28$	
Red cell count	$\leq 0.84 \times \text{LL}$	

Parameter	Toxicity Decrease	Toxicity Increase
Mean corpuscular volume	$\leq 0.84 \times LL$	$\geq 1.11 \times UL$
Mean corpuscular hemoglobin	$\leq 0.84 \times LL$	
Mean corpuscular hemoglobin concentration	$\leq 0.84 \times LL$	
Platelets ( $\times 10^9/L$ )	$\leq 74$	
Prothrombin time		$> 1.5 \times UL$
Prothrombin international normalized ratio		$> 1.5$
Total white blood cell count ( $\times 10^9/L$ )	$\leq 2.9$	$\geq 21$
Total neutrophil count ( $\times 10^9/L$ )	$\leq 1.36$	$\geq 14.7$
Segmented neutrophil count ( $\times 10^9/L$ )	$\leq 0.75$	$\geq 12.3$
Eosinophils ( $\times 10^9/L$ )		$\geq 1.5$
Basophils ( $\times 10^9/L$ )		$\geq 0.31$
Monocytes ( $\times 10^9/L$ )		$\geq 2.1$
Lymphocytes ( $\times 10^9/L$ ) for patients <18 years (auto hematology)	$\leq 1.0$	
Lymphocytes ( $\times 10^9/L$ ) for patients <18 years (manual hematology)	$\leq 0.2$	
Lymphocytes ( $\times 10^9/L$ ) for patients $\geq 18$ years	$\leq 0.2$	

UL = upper limit of reference range      LL = lower limit of reference range

## Appendix 5 List of Tables, Listings and Figures

Lists of the tables, listings and figures to be provided are given below in [Table 13](#), [Table 14](#) and [Table 15](#), respectively.

